## 5.0 STUDY PROCEDURES

Visit Number	1	2	3	4	5	6	7	8	9	10	11	x	x + 1	x + 2	x + 3	x + 4
Procedure/Study Day	SV 	D1	D14 (±3D)	W4 (±3D)	W8 (±3D)	W12 (±3D)	W16 (±3D)	W18 (±3D)	W20 ** (±3D)	W22 (±3D)	W24 (±3D)	Off Treatm ent 	3M (±1 month)	6M ±1 month)	9M (±1 month)	12M + q6M (±1 month)
Informed consent	X															
Durvalumab 1500mg		X		X	X											
Durvalumab 750mg							X	X	X	X	X					
Tremelimumab 75mg		X		X	X	X										
CT chest, abdomen, pelvis; nuclear bone scan 	X				X		X				X	X				
Assessment of AEs/SAEs 		X	X	X	X	X	X	X	X	X	X	X	X			
Concomitant medications (including next line therapy after off treatment, response)	X	X	X	X	X	X	X	X	X	X	X	X	X			
Physical examination  , weight	X		X	X	X	X	X		X		X	X	X	X	X	
Height (prior to dosing)	X															
ECOG performance status	X			X	X	X	X		X		X	X	X	X	X	
12-lead Electrocardiogram 	X															
Vital signs 	X	X	X	X	X	X	X	X	X	X	X	X				
Urinalysis 	X															
Hepatitis serologies 	X															
HIV antibody	X															
Pregnancy test 	X															
Serum chemistry 	X	X	X	X	X	X	X	X	X	X	X	X	X			
lactate dehydrogenase, GGT, lipase, uric acid and amylase 	X	X	X	X	X	X					X	X				
Hematology 	X	X	X	X	X	X	X	X	X	X	X	X	X			
Coagulation parameters 	X			X	X							X				
Thyroid function tests 	X	X		X	X	X					X	X				
Research blood samples 	X				X							X 				
Tumor biopsy 	X				X						X					

**\*\* Visits 8 through 11 will repeat for a total of up to 18 doses of durvalumab, or until progressive disease (see 4.1.1) or unacceptable toxicity, with CTs and bone scan done every 8 weeks.** Scans are to be completed every 8 weeks, regardless of drug holds or treatment delays. (Note: Bone scans will be done only if the patient has bone disease. PET-CT is acceptable in place of bone scan, if a bone scan is contra-indicated for a patient's disease. The same modality used at baseline should be used throughout). Patients may continue on therapy after progression or after initial 52 week treatment period as specified in Sections 4.1.1 and 4.1.2. Abbreviations: SV (screening visit)

 The same modality used at baseline should be used throughout. CT must have contrast, MRI with contrast is acceptable alternative if the patient is allergic to CT contrast. Scans are required to be completed every 8 weeks, regardless of drug holds or treatment delays.

(Note: Bone scans will be done only if the patient has bone disease. PET-CT is acceptable in place of bone scan, if a bone scan is contra-indicated for a patient's disease. The same modality used at baseline should be used throughout.) For patients with skin lesions, photographs may be taken on study-provided camera by study staff on a white background (wall of patient room) using a ruler measurement on a study supplied digital camera. Photographs should not include any identifying characteristics. (Please refer to section 6.1.1 for details)

 Urinalysis will include color, appearance, specific gravity, pH, protein, glucose, ketones, blood, bilirubin, and microscopy including WBC/high power field (HPF), RBC/HPF.

 Serum beta-human chorionic gonadotropin (at screening only) for females of child-bearing potential (as indicated) within 7 days of registration.

 Serum Chemistry Panel will include calcium, chloride, magnesium, creatinine, sodium, potassium, blood urea nitrogen, bicarbonate, glucose, total bilirubin, aspartate aminotransferase (AST), alanine aminotransferase (ALT), alkaline phosphatase (ALP), albumin, total protein and creatinine clearance. If Total bilirubin is  $\geq 2 \times \text{ULN}$  (and no evidence of Gilbert's syndrome) then fractionate into direct and indirect bilirubin. Additional chemistry labs will include: lactate dehydrogenase (LDH), GGT, lipase, uric acid and amylase. During combination therapy, these labs should be monitored prior to each dose; during maintenance monotherapy, labs should be monitored every 8 weeks.

 Hematology will include basophils, eosinophils, lymphocytes, platelet count, monocytes, neutrophils, red blood cell count, total white cell count, hematocrit, mean corpuscular hemoglobin, mean corpuscular hemoglobin concentration, mean corpuscular volume, and hemoglobin.

 Coagulation parameters will include prothrombin time, partial thromboplastin time, and fibrinogen.

 Thyroid function tests will include thyroid stimulating hormone, free T3, and free T4. During combination therapy, these labs should be monitored prior to each dose; during maintenance monotherapy, labs should be monitored every 8 weeks.

 Patients will be followed by routine clinic visit or phone call at 3, 6, 9, 12 months and then every 6 months for 3 years total from the end of treatment to document survival and disease progression.

 The maximum time interval between Screening Visit/ baseline study procedures and the first dose of study drug will be 14 days. Systemic imaging (CTs, bone scan or PET-CT) and consent may be performed up to 28 days prior. Note: Bone scans will be done only if the patient has bone disease. PET-CT is acceptable in place of bone scan, if a bone scan is contra-indicated for a patient's disease. The same modality used at baseline should be used throughout.

 Full physical examinations will include assessments of the head, eyes, ears, nose, and throat and the respiratory, cardiovascular, GI, urogenital, musculoskeletal, neurological, dermatological, hematologic/lymphatic, and endocrine systems. Height will be measured at screening only. Targeted physical examinations are to be utilized by the Investigator on the basis of clinical observations and symptomatology. Situations in which physical examination results should be reported as AEs are described in Section 10

 Resting 12-lead ECGs (x2, 5 minutes [+/- 2 min] apart) will be recorded at screening and as clinically indicated throughout the study. ECGs should be obtained after the patient has been in a supine position for 5 minutes and recorded while the patient remains in that position. At Screening, 2 ECG's will be obtained on which QTcF must be  $< 470$  ms. In case of clinically significant ECG abnormalities, including a QTcF value  $> 470$  ms, 2 additional 12-lead ECGs should be obtained over a brief period (eg, 30 minutes) to confirm the finding.

- 12 Vital signs (blood pressure [BP], pulse, temperature) will be evaluated according to the assessment schedules outlined in Section 4.2.1).
- 13 Hepatitis A antibody, hepatitis B surface antigen, hepatitis C antibody
- 14 80 mL of whole blood should be collected in eight 10 mL plastic lavender top tubes (K2EDTA)
- 15 AE/SAE will be recorded from time of signature of informed consent, throughout treatment period, including the follow-up period (90 days after the last dose of durvalumab/tremelimumab)
- 16 tumor biopsy is mandatory prior to study enrollment and after 2 cycles of treatment (as clinically appropriate by PI discretion). At progression patients will be offered an optional biopsy. *(Note: If it is felt to be clinically inappropriate to biopsy the patient, then this should be clearly documented in the patient's chart and CRF. This documentation should also be printed and flagged in the patient's research chart).*
- 17 On each treatment day, hematology and serum chemistry are to be resulted before treatment can begin.

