### **2.3 Exploratory Objectives & Endpoints**

2.3.1 To evaluate if serum and tissue-based biomarkers including: circulating tumor DNA, immunohistochemical expression of PD-L1; tumor infiltrating lymphocytes (TILs); changes in tissue and peripheral T cell receptor genotype; mutational and neoantigen burden; and immune-related candidate gene expression signatures predict response to durvalumab in combination with tremelimumab.

2.3.2. To determine the response rate (RR) and duration of response(DoR) of subsequent next line therapy after progression on durvalumab/ tremelimumab study regimen, for those patients who are able to submit detailed follow up data about subsequent treatment and response.

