**4.1.2 Continuation of Investigational Therapy after 52 Weeks**

- Patients who achieve clinical benefit (CR, PR, or SD) until the end of the 52 week period may enter a follow up phase or continue durvalumab as shown in table 5.1 for up to 52 more weeks as long as they are felt to be deriving clinical benefit.
- Patients who enter follow up phase will continue to be monitored. If during the first 6 months of follow-up, patients developing PD may be re-treated with

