#### 4.7 Duration of Follow Up

After patients come off treatment they will be followed up at 3, 6, 9, 12 months and then every 6 months for 3 years for survival and progression of disease.

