#### **7.1 Adverse Event Monitoring**

Adverse event data collection and reporting, which are required as part of every clinical trial, are done to ensure the safety of subjects enrolled in the studies as well as those who will enroll in future studies using similar agents. Adverse events are reported in a routine manner at scheduled times during a trial (see Section 5 for time points). In addition, certain adverse events must be reported in an expedited manner to allow for optimal monitoring and patient safety and care.

All patients experiencing an adverse event, regardless of its relationship to study drug, will be followed until:

- the adverse event resolves or the symptoms or signs that constitute the adverse event return to baseline;
- any abnormal laboratory values have returned to baseline;
- there is a satisfactory explanation other than the study drug for the changes observed; or
- death.

Adverse events and serious adverse events will be recorded from time of signature of informed consent, throughout the treatment period and including the follow-up period (90 days after the last dose of durvalumab + tremelimumab, or until resolution of AEs).

**During the course of the study all AEs and SAEs should be proactively followed up for each subject. Every effort should be made to obtain a resolution for all events, even if the events continue after discontinuation/study completion.**

If a subject discontinues from treatment for reasons other than disease progression, and therefore continues to have tumor assessments, drug or procedure-related SAEs must be captured until the patient is considered to have confirmed PD and will have no further tumor assessments.

The investigator is responsible for following all SAEs until resolution, until the subject returns to baseline status, or until the condition has stabilized with the expectation that it will remain chronic, even if this extends beyond study participation.

AstraZeneca/MedImmune retains the right to request additional information for any subject with ongoing AE(s)/SAE(s) at the end of the study, if judged necessary

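### The Section 5.0 schedule stops recording next-line therapy at 3 months and sets no imaging after treatment ends, although Sections 2.3.2, 4.1, 7.1, 7.3.3.5 and 10.3 rely on those data

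*Combined protocol and SAP*

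**What the plan says.** **Follow-up.** Section 4.7 sets contacts at 3, 6, 9 and 12 months, "then every 6 months for 3 years for survival and progression of disease". Footnote 8 in Section 5.0 gives the same timetable and allows either mode of contact: "Patients will be followed by routine clinic visit or phone call at 3, 6, 9, 12 months and then every 6 months for 3 years".

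**Imaging.** The row "CT chest, abdomen, pelvis; nuclear bone scan" is marked at screening, W8, W16, W24 (repeating every 8 weeks on treatment) and Off Treatment. It is blank at 3M, 6M, 9M and 12M+q6M. The interval rule reads "Scans are to be completed every 8 weeks, regardless of drug holds or treatment delays". It covers interruptions of treatment, not the time after treatment has ended.

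**Next-line therapy.** These data share a row with concomitant medications: "Concomitant medications (including next line therapy after off treatment, response". The row is marked from screening to 3M and is blank afterwards. The change log in Appendix E records that concomitant-medication review was taken out of the 6-, 9- and 12-month visits, so the blanks are intended.

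**What other sections expect.**
- Section 2.3.2: "To determine the response rate (RR) and duration of response(DoR) of subsequent next line therapy after progression". Section 4.1 says next-line therapy will be monitored. Section 10.3 measures duration from next-line therapy to its last dose, by Kaplan-Meier.
- Section 4.8 lists the start of another anticancer therapy among the events after which there is no further study observation.
- Section 7.1, repeated in 7.3.3.5: "If a subject discontinues from treatment for reasons other than disease progression, and therefore continues to have tumor assessments".
- Section 4.1.2: "If during the first 6 months of follow-up, patients developing PD may be re-treated with" durvalumab.
- Section 10.3 censors PFS for living patients at the last tumour assessment. Death without progression is an event.

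**The concern.** The schedule is what sites follow. If a data item is not marked there, it is collected only when someone happens to obtain it.

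For next-line therapy, the collection window closes about when a first restaging on the new treatment would be read. Responses seen later, and most last-dose dates, then depend on records that patients submit. Section 4.8, read literally, closes the window at the very event that the objective starts from. It would also end the survival follow-up promised in Section 4.7.

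For PFS, the patients affected are those who stop for toxicity or who finish 52 weeks in benefit and enter follow-up. On treatment, progression is dated by 8-weekly scans. Afterwards it is dated by whatever imaging happens, or by a contact that may be a phone call. Late detection lengthens PFS, and censoring the living at the last scan while counting deaths treats the two groups differently.

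**Working it through.** The plan gives no figure to reproduce here. The check is a count of the schedule, a timing grid, and an illustration of the PFS rule.

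**1. Contacts.** Months 3, 6, 9, 12, 18, 24, 30 and 36 after treatment make 8 contacts. Imaging is marked at 0 of 8. Next-line therapy and response are marked at 1 of 8. With the ±1 month window, the 3M contact falls at 2 to 4 months, or 2 × 52/12 = 8.7 to 4 × 52/12 = 17.3 weeks.

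**2. Next-line response.** Assume next-line therapy starts 2, 4, 8 or 12 weeks after stopping and is first scanned 8 or 12 weeks later. The documents give neither figure. Week in which the first result is known:

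| Start (weeks) | Scan +8 | Scan +12 |
|---|---|---|
| 2 | 10 | 14 |
| 4 | 12 | 16 |
| 8 | 16 | 20 |
| 12 | 20 | 24 |

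By week 13, 2 of 8 combinations are known. By week 17.3, the latest permitted 3M contact, 5 of 8 are. The other 3 have no scheduled collection. Nor does any patient whose progression and new therapy come after that contact.

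**3. Next-line duration.** The longest duration that a scheduled contact can record is 17.3 − 2 = 15.3 weeks for a start at week 2, and 17.3 − 12 = 5.3 weeks for a start at week 12. Kaplan-Meier can censor these patients, but the curve carries no scheduled information beyond about 4 months.

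**4. PFS illustration.** All inputs are assumptions:
- exponential time to progression with median 4, 8 or 12 months;
- exponential time from progression to death with median 9 months;
- 10% or 30% assigned an early stop, uniform over months 1 to 12 and effective only if progression has not occurred, with everyone else stopping at month 12;
- no progression found after stopping (the worst case);
- deaths up to month 36 counted, and the living censored at the stop.

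True 18-month PFS is 0.5^(18/median). The reading is a Kaplan-Meier estimate from 100,000 simulated patients.

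| Median (months) | True | As read (10% to 30% early stop) |
|---|---|---|
| 4 | 0.04 | 0.10 to 0.12 |
| 8 | 0.21 | 0.30 to 0.31 |
| 12 | 0.35 | 0.43 |

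Between 15% and 56% stop without progression. If deaths were not counted and all were censored at the off-treatment scan, nobody would be at risk after month 12.

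The direction is not fixed over the whole curve. Under these rules everyone still at risk after month 12 is someone who dies by month 36, so the curve must reach 0 by then. The true value is 0.5^(36/12) = 0.125 at a 12-month median. The upward error belongs to the middle of the curve.

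**The case against.** The strongest reply is that blank cells do not prove non-collection. The table has no row for survival or progression at all, and its 12M+q6M column is empty throughout, so footnote 8 carries the follow-up outcomes rather than the marks. Sections 4.7 and 4.8 plan progression follow-up. Physical examination and ECOG status are marked at 3M, 6M and 9M, and Section 4.8 offers phone contact as an alternative for patients who decline to return. Table 5.1 has a scan at re-evaluation before re-treatment. Objective 2.3.2 is exploratory and limited to patients able to submit data, Section 10.3 accepts outside radiograph reports, and duration needs only treatment dates. PFS is secondary in a single-arm trial, so no between-arm bias arises.

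Most of this stands, and it limits the point. A reader might infer that PFS and objective 2.3.2 cannot be measured as defined. The documents do not support that: documented progression has a route, censored PFS is computable, and submitted records can supply next-line data. A reader might also infer that ORR suffers through delayed responses after early stopping. Section 1.7.2 uses delayed response to justify maintenance treatment and does not predict responses after a toxicity stop. ORR rests mainly on scheduled on-treatment scans.

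The reply does not remove the gap. No section gives a scan interval after treatment. The table 5.1 scan comes once re-treatment is already in view. Footnote 8 lets a phone call document progression for anyone. The reply also leaves Section 4.8 in conflict with Sections 2.3.2 and 4.1.

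**Conclusion.** The point holds as a mismatch between the schedule and the sections that depend on it.

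Next-line therapy is the clearer part. Collection is scheduled at 1 of 8 contacts, and Section 4.8 contradicts the objective. Response rate may be understated if patients without a recorded response stay in the denominator, and duration is truncated at about 4 months after stopping, apart from records that patients happen to submit.

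For PFS, the estimate after a stop without progression rests on unscheduled imaging and may be biased upward. The illustrated error at 18 months is about 0.06 to 0.10. That is a worst case under assumed inputs, since any scan done in practice shrinks it.

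How many patients are affected is not known. Applying the 3/24 treatment-related discontinuations from the lung cancer study in Section 1.3 to 50 planned patients gives 0.125 × 50, about 6. A reader might take that as an estimate. It is only an assumption: the disease differs, not every such patient stops progression-free, 11 of the first 18 evaluable patients here had progression as their recorded response (Section 1.7.3), and Appendix E notes closure for low accrual.

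**What to change.** **Next-line data.** Separate next-line therapy, response, and first and last dose dates from the concomitant-medication row. Mark them at 3M, 6M, 9M, 12M and every 6 months. The contacts already exist, and a phone call is enough for these items. Reword Section 4.8 so that starting another anticancer therapy, which already ends study treatment there, also ends PFS assessment but not the collection of survival and next-line data. Add the matching PFS censoring rule for new therapy to Section 10.3.

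**Progression.** Reconcile the Section 5.0 table and footnote 8 with Sections 7.1 and 7.3.3.5: state whether and when tumour assessments continue after a stop without progression, until progression or new therapy. At the existing contacts, collect the dates and reports of routine restaging scans. State that a phone report alone does not date progression.

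**Cost.** Wording in one table, two footnotes or sections and Section 10.3, and slightly more data collection. Additional mandatory scans are not required for this fix. For patients whose contacts have passed, the same items can be sought from records, and the report should say how progression after treatment was ascertained.

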## 5.1 Study Procedures After 52 Weeks of study treatment

(For patients who are continuing treatment or re-starting treatment after progression of disease after 52 weeks, this table should not be used for patients who stay on therapy due to pseudoprogression)

Visit Number		1	2	3	4	5	6
Procedure/Study Day	Re-Evaluation before re-treatment	D1 **	D14 (±3D)	W4 (±3D)	W6 (±3D)	W8 *** (±3D)	
Durvalumab 750mg*		X	X	X	X	X	
CT chest, abdomen, pelvis; nuclear bone scan 	X					X	
Assessment of AEs/SAEs	X	X	X	X	X	X	
Concomitant medications	X	X	X	X	X	X	
Physical examination  , weight	X	X	X	X	X	X	
ECOG performance status	X	X	X	X	X	X	
Vital signs 	X	X	X	X	X	X	
Serum chemistry 	X	X		X		X	
lactate dehydrogenase, GGT, lipase, uric acid and amylase 	X	X				X	
Hematology 	X	X		X		X	
Coagulation parameters 	X	X				X	
Thyroid function tests 	X	X				X	

\* Treatment for this patient population will be Durvalumab monotherapy. On each treatment day, hematology, serum chemistry are to be resulted before treatment can begin.

\*\* The maximum time interval between re-evaluation study procedures and the first dose of study drug will be 14 days

\*\*\* Visits 2 through 6 will repeat for a total of up to 26 doses of durvalumab (52 weeks of therapy total), or until progressive disease (see 4.1.1) or unacceptable toxicity, with CTs and bone scans done every 8 weeks. Scans are to be completed every 8 weeks, regardless of drug holds or treatment delays.

 The same modality used at initial baseline should be used. Scans to be completed every 8 weeks, regardless of drug holds or treatment delays.

Note: Bone scans will be done only if the patient has bone disease. PET-CT is acceptable in place of bone scan, if a bone scan is contra-indicated for a

patient's disease. The same modality used at baseline should be used throughout. For patients with skin lesions, photographs may be taken on study-provided camera by study staff on a white background (wall of patient room) using a ruler measurement on a study supplied digital camera. Photographs should not include any identifying characteristics

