### 7.2.3 Serious Adverse Events (SAEs)

All SAEs, regardless of attribution, occurring from time of signed informed consent, through 30 days after the last administration of study drug, must be reported upon discovery or occurrence.

An SAE is defined in regulatory terminology as any untoward medical occurrence that:

- **Results in death.**  
If death results from (progression of) the disease, the disease should be reported as event (SAE) itself.
- **Is immediately life-threatening.**  
The patient was at risk of death at the time of the event; it does not refer to an event that hypothetically might have caused death if it were more severe.
- **Requires *in-patient hospitalization or prolongation of existing hospitalization for ≥ 24 hours.***
- **Results in persistent or significant disability or incapacity.**
- **Is a congenital anomaly/birth defect.**
- **Is an important medical event.**

Any event that does not meet the above criteria, but that in the judgment of the investigator jeopardizes the patient, may be considered for reporting as a serious adverse event. The event may require medical or surgical intervention to prevent one of the outcomes listed in the definition of "Serious Adverse Event".

For example: allergic bronchospasm requiring intensive treatment in an emergency room or at home; convulsions that may not result in hospitalization; development of drug abuse or drug dependency.

The causality of SAEs (their relationship to all study treatment/procedures) will be assessed by the investigator(s) and communicated to AstraZeneca.

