#### **7.3.3.4 Reporting to MedImmune**

All deaths that occur during the study, or within the protocol-defined 30-day

post-last dose of durvalumab + tremelimumab safety follow-up period must be reported to AstraZeneca as follows:

- Death that is clearly the result of disease progression should be documented but should not be reported as an SAE.
- Where death is not due (or not clearly due) to progression of the disease under study, the AE causing the death must be reported to AstraZeneca as a SAE within **24 hours** (see Section **Error! Reference source not found.** for further details). The report should contain a comment regarding the co-involvement of progression of disease, if appropriate, and should assign main and contributory causes of death.
- Deaths with an unknown cause should always be reported as a SAE.

All SAEs will be reported, whether or not considered causally related to the investigational product, or to the study procedure(s). The reporting period for SAEs is the period immediately following the time that written informed consent is obtained through 90 days after the last dose of durvalumab + tremelimumab or until the initiation of alternative anticancer therapy. The investigator and/or Sponsor are responsible for informing the Ethics Committee and/or the Regulatory Authority of the SAE as per local requirements.

The investigator and/or sponsor must inform the FDA (as outlined above), of any serious or unexpected adverse events that occur in accordance with the reporting obligations of 21 CFR 312.32, and will concurrently forward all such reports to AstraZeneca. A copy of the MedWatch report must be faxed to AstraZeneca at the time the event is reported to the FDA. It is the responsibility of the sponsor to compile all necessary information and ensure that the FDA receives a report according to the FDA reporting requirement timelines and to ensure that these reports are also submitted to AstraZeneca at the same time.

A **cover page** should accompany the **MedWatch** form indicating the following:

- “Notification from an Investigator Sponsored Study”
- The investigator IND number assigned by the FDA
- The investigator’s name and address
- The trial name/title and AstraZeneca ISS reference number (ESR-14-10694 (D4190C00030)

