### **7.3.3.5 Study recording period and follow-up for adverse events and serious adverse events**

Adverse events and serious adverse events will be recorded from time of signature of informed consent, throughout the treatment period and including the follow-up period (90 days after the last dose of durvalumab + tremelimumab).

During the course of the study all AEs and SAEs should be proactively followed up for each subject. Every effort should be made to obtain a resolution for all events, even if the events continue after discontinuation/study completion.

If a subject discontinues from treatment for reasons other than disease progression, and therefore continues to have tumor assessments, drug or procedure-related SAEs must be captured until the patient is considered to have confirmed PD and will have no further tumor assessments.

The investigator is responsible for following all SAEs until resolution, until the subject returns to baseline status, or until the condition has stabilized with the expectation that it will remain chronic, even if this extends beyond study participation.

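### The schedule does not guarantee adverse-event ascertainment to day 90: the last AE-marked contact may fall at about day 60, and Table 5.1 has no post-treatment column or cross-reference

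*Combined protocol and SAP*

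**What the plan says.** **Recording period.** Footnote 15 to the Section 5.0 table, attached to the AE/SAE row, starts recording at consent and continues it through treatment, "including the follow-up period (90 days after the last dose of durvalumab/tremelimumab". Section 7.3.3.5 says the same: "including the follow-up period (90 days after the last dose of durvalumab + tremelimumab". Section 7.1 gives "90 days after the last dose of durvalumab + tremelimumab, or until resolution of AEs". For SAEs reported to the drug supplier, Section 7.3.3.4 runs "through 90 days after the last dose of durvalumab + tremelimumab or until the initiation of alternative anticancer therapy".

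**Section 5.0 table.** The AE row is marked from Day 1 to the Off Treatment column and once more at 3M. The 6M, 9M and 12M columns are blank in that row. The 3M column has a window of ±1 month. Under footnote 8 the follow-up contacts may be clinic visits or phone calls, and they run "for 3 years total from the end of treatment to document survival and disease progression".

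**Table 5.1.** This grid serves patients who continue or restart durvalumab after 52 weeks. It marks AE assessment at re-evaluation and at every treatment visit; "Visits 2 through 6 will repeat for a total of up to 26 doses of durvalumab (52 weeks of therapy total". It has no off-treatment or post-treatment column, its AE row does not carry footnote 15, and it does not refer to Section 4.7 or 4.8.

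**A different SAE period.** Section 7.2.3 requires SAEs from consent "through 30 days after the last administration of study drug, must be reported upon discovery or occurrence".

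**The concern.** A 90-day recording period needs someone to ask about events at or after day 90. The plan schedules one AE-marked contact after the Off Treatment visit and allows it a month early. The change log in Appendix E suggests how this came about: Amendment 3 widened the follow-up windows from ±7 days to ±1 month, and Amendment 10 removed the AE checks at 6, 9 and 12 months to match the 90-day rule. The 3M contact was thus left to close the period alone, and its early allowance stayed.

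Safety and tolerability is a secondary objective (Section 2.2.2), summarised as number, frequency and severity of AEs. Section 7.2.5.11 warns that immune-related events could be more frequent with the combination than with either drug alone. If the closing enquiry is at day 60 for one patient and day 120 for another, the two do not have equal ascertainment within the nominal 90 days.

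**Working it through.** There is no sample-size or error-rate figure to reproduce. The check is calendar arithmetic on the schedule.

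**Inputs**
- Recording period: 90 days after the last dose (Section 5.0 footnote 15; Sections 7.1 and 7.3.3.5).
- Last AE-marked contact: 3 months ±1 month (Section 5.0 table).
- Starting point: end of treatment (footnote 8). The documents do not time the Off Treatment visit relative to the last dose, so the gap *g* between last dose and end of treatment is an assumption: 0, 14 or 28 days.

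**Step 1. Months to days, over every start date in 2019 and 2020**

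| Contact | Shortest | Mean | Longest |
|---|---|---|---|
| 3M − 1 month | 59 | 60.9 | 62 |
| 3M nominal | 89 | 91.4 | 92 |
| 3M + 1 month | 120 | 121.8 | 123 |
| 6M − 1 month (not marked for AEs) | 150 | 152.3 | 153 |

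The nominal visit meets the 90-day period to within a day. The early edge of the window does not.

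**Step 2. Largest shortfall**, taking two months as 60 days: earliest contact = 60 + *g*; shortfall = 90 − (60 + *g*).

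| *g* (days) | Earliest contact | Days with no scheduled AE enquiry |
|---|---|---|
| 0 | day 60 | 90 − 60 = 30 |
| 14 | day 74 | 90 − 74 = 16 |
| 28 | day 88 | 90 − 88 = 2 |

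With *g* = 0 the shortfall is 30/90, one third of the period. By calendar it is 90 − 62 = 28 to 90 − 59 = 31 days. The window is symmetric, so a late visit may equally fall at about day 120, which covers the period in full.

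**Step 3. Patients on Table 5.1.** Section 4.7 sets contacts at 3, 6, 9 and 12 months after treatment stops and does not exclude extension or re-treated patients. Its stated purpose is survival and progression. Section 4.8 says that patients who permanently discontinue are in general followed for safety as well, and offers 3-monthly phone follow-up to those who decline to return. So contact is provided for, but nothing in Table 5.1 tells the site that an AE assessment belongs to it or when it is due.

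**Step 4. After the change.** If the closing AE contact may not precede day 90 from the last dose, the shortfall is 0. Moving the window to 3 months with no early allowance is not quite enough: 1 February to 1 May in a non-leap year is 28 + 31 + 30 = 89 days.

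**The case against.** The strongest reply is that the duty to record to 90 days does not depend on the visit grid. Footnote 15 sits on the AE row itself, Sections 7.1 and 7.3.3.5 repeat the period without tying it to a visit, and both add a general duty: "During the course of the study all AEs and SAEs should be proactively followed up for each subject". Section 7.3.2 also requires reporting of attributed events that arise more than 30 days after the last dose. Physical examination and performance status remain marked at 6M and 9M, so an event that began between days 61 and 90 could still come to light.

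Much of this stands, and it rules out three stronger readings.

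- A reader might infer that the 90-day period cannot be delivered. It can: the nominal visit is at about day 91 and the window runs to about day 120. What is missing is a guarantee.
- A reader might infer that late immune events are in fact undercounted. The documents give neither a late-onset rate nor a distribution of visit timing, so this is a possibility and not a finding.
- A reader might infer that patients leaving treatment from Table 5.1 have no follow-up. Sections 4.7 and 4.8 provide it; the table lacks a column or cross-reference.

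What does not stand is that the general duty makes the schedule irrelevant. The follow-up text aims chiefly at obtaining resolution of events. A non-serious event starting on day 70 is recorded only if someone asks or the patient volunteers it, and the next scheduled contact, at about day 150 or later, is not marked for AEs.

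It is also fair to say that safety here is a secondary, descriptive endpoint in a single-arm trial, so no between-arm comparison is biased.

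**Conclusion.** The point holds as a schedule gap. An on-protocol 3M contact may leave up to about 30 of the 90 days with no scheduled AE enquiry when counted from the last dose, or 2 to 16 days if end of treatment is 28 to 14 days later. The first basis agrees with the Amendment 10 entry in Appendix E, which places the 3-month visit after the last dose; the second rests on an assumed timing of the Off Treatment visit. The likely loss is mainly of non-serious late events, because SAEs have their own reporting rules. Its size cannot be estimated from the documents.

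Two neighbouring passages bear on the same period. Section 7.2.3 limits SAE reporting to 30 days while Section 7.3.3.4 gives 90 days or the start of other anticancer therapy. Section 4.8 ends study observation when other anticancer therapy starts, which may come before day 90.

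This is a modest but worthwhile correction. Appendix E (Amendment 12) records that the study closed on 7.20.2020 for low accrual, so a change to the schedule helps only patients still on treatment or in follow-up.

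**What to change.** 1. In the Section 5.0 table, require the closing AE contact no earlier than day 90 after the last dose, for example day 90 to +1 month. State the limit in days from the last dose, since three calendar months can be 89 days. Footnote 8 already allows a phone call.
2. In Table 5.1, state that the Off Treatment and 3M AE assessments of the Section 5.0 table apply to extension and re-treated patients, with a reference to Sections 4.7 and 4.8.
3. Reconcile the 30-day SAE text in Section 7.2.3 with the 90-day rule in Sections 5.0, 7.1, 7.3.3.4 and 7.3.3.5, and say how AE recording to day 90 relates to the end of observation under Section 4.8.
4. For patients whose 3M visit has already taken place early, report the date of the last AE contact with the safety summary so that the length of ascertainment is visible.

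The cost is a few edits to tables and text and slightly less scheduling flexibility for one contact.
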